5.3. Exclusion Criteria

Subjects meeting one or more of the following exclusion criteria are not to be enrolled in the study:

1. The subject has been withdrawn or discontinued prematurely from either TEN-01-301 or TEN-01-302

2. The subject reports using any prohibited medication and is not willing to abide by the restrictions for intake
3. Pregnant or lactating women.
4. If, in the opinion of the Investigator the subject is unable or unwilling to fulfill the requirements of the protocol or has a condition, which would render the results uninterpretable..

5.4. Rescue Medication

Rescue medications are allowed for severe constipation (i.e, at least 72 hours after the subject's previous BM or when symptoms become intolerable). Bisacodyl (5 mg tablet or 10 mg suppository) is the preferred rescue medication; however, other rescue medications prescribed by a physician as standard of care are allowed.

5.5. Prohibited Concurrent Medications

The following medications are specifically prohibited from use during the study, unless specified as a rescue medication.

All prescription and/or over the counter medications used to treat constipation and/or IBS-C (e.g., linzess, amitiza, miralax, dulcolax, lactulose, bisacodyl).

Narcotics either alone or in combination (e.g., tramadol, codeine, morphine, propoxyphene, loperamide, diphenoxylate, paregoric) if they are being used chronically and are expected to be taken indefinitely in the future.

Patient is planning to receive an investigational drug (other than study drug) or investigational device at any time during this study (any investigational or imported drugs that have not been approved for human use by the FDA)

5.6. Removal of Subjects from Therapy or Assessment

Subjects will be discontinued from the study if a subject experiences a study drug related serious adverse event.

Subjects will be informed that they can withdraw from the study at any time for any reason, without prejudice to their medical care. The Investigator may remove a subject if he/she feels this action is in the best interest of the subject.

When a subject withdraws from the study, all of the necessary safety and tolerability assessments as described for Visit 4 should be obtained. Subjects experiencing adverse reactions should be followed until the reaction has resolved or is clearly determined to be due to a subject's stable or chronic condition. Appropriate supportive and/or definitive therapy will be administered as required.

The reason(s) for a subject's withdrawal from the study and their final assessments are to be recorded on the appropriate electronic case report form (eCRF) page.

6. TREATMENTS

6.1. Identity of Investigational Product

Tenapanor (as the dihydrochloride salt) drug product will be supplied as white to off-white oval biconvex film-coated tablets.

6.2. Packaging, Storage, and Labeling

The study drug will be supplied in white square HDPE bottles with child resistant polypropylene (CRC) closures with an induction seal plus desiccants. Each bottle will contain sixty-six (66) tenapanor 50 mg tablets.

Tenapanor tablets should be stored in the original packaging between 2°C and 30°C. Temperature excursions are allowed from -30°C to 50°C for a maximum of 1 week.

6.3. Treatments to be Administered

Study drug will be dispensed only to eligible subjects under the supervision of the Investigator or identified sub-Investigator(s). All eligible subjects will receive tenapanor 50 mg BID. Subjects will take one tenapanor tablet twice daily, immediately prior to breakfast or the first meal of the day and immediately prior to dinner.

Subjects will receive three bottles of drug at Visit 1 (Day 1) and Visit 2 (Week 13 ± 2). If the subject was previously in study TEN-01-301, they will also receive three bottles of drug at Visit 3 (Week 26 ± 2). At each visit the subject will be asked to return their unused drug and bottles. Study drug compliance will be monitored by the clinical site staff and will be verified by the study monitor during on-site monitoring visits.

6.4. Randomization and Blinding

This is an open label study. There is no randomization and all subjects and study personnel are unblinded. All subjects that enroll in this study will receive tenapanor 50 mg BID.

7. SCHEDULE OF ASSESSMENTS

The study flow chart, including all procedures to be performed during the study is presented below. Prior to engaging in any study procedure, each subject must sign and date an informed consent form. In addition, a telephone contact will take place as footnoted below to find out if any treatment related problems have occurred. Additional telephone calls to the subjects for treatment follow-ups of AEs will be made as needed.

Evaluation	Enroll ^a	Treatment Period ^c		
		1	2	3 ^b
Site Visit ^h	1	2	3 ^b	4/ET ^c
Study Week(s)	1	13±2	26±2	39±2
Informed Consent ^a	X			
Inclusion/Exclusion	X			
Concurrent Medications		X	X ^{b#}	X
Physical Exam			X ^b	X
Vital Signs ^d		X	X ^{b#}	X
Safety Laboratories ^f			X ^b	X
Urine Pregnancy test ^{fg}		X	X ^b	X
Urinalysis ^f			X ^b	X
12-lead electronic ECG			X ^b	X
Drug Dispensed/returned	D	D/R	D [#] /R ^{b#}	R
Adverse Event Assessments		X	X ^{b#}	X

^aThe Informed Consent Form (ICF) must be signed before any protocol procedures are performed.

^bThis is the final visit for subjects that enrolled from Protocol TEN-01-302 and only procedures with this footnote are performed on subjects from TEN-01-302. Procedures for subjects enrolled from Protocol TEN-01-301 are marked with a #

^cThis is the final visit for subjects that enrolled from Protocol TEN-01-301. It is also used as an early termination (ET) visit.

^dVital signs include systolic and diastolic blood pressure (seated), heart rate, respiratory rate, temperature and body weight.

^eWhen a subject discontinues early, procedures performed at Visit 4 should be performed at the subject's last visit.

^fLaboratory assessments are detailed in Appendix A

^g If the urine pregnancy test is positive, it will be confirmed with a serum pregnancy test.

^hTelephone calls will be made to subjects monthly during the two months prior to a site visit to ascertain if there have been any treatment related problems (Weeks 5±1, 9±1, 17±1, 22±1 for subjects from TEN-01-301 and TEN-01-302 and for subjects from TEN-01-301 also Weeks 30±1 and 35±1).

8. STUDY EVALUATIONS

The assessments to be performed during the study are outlined by visit and study day/week below. The day of enrollment begins the clock for all subsequent visit days and dates.

8.1. Evaluations and procedures at Visit 1 (Day 1)

The following procedures will be conducted at Visit 1:

- Informed Consent
- Inclusion/Exclusion Criteria
- Drug Dispensed

8.1.1 Telephone contacts (Weeks 5±1, 9±1, 17±1, 22±1, for subjects from TEN-01-301 also Weeks 30±1 and 35±1)

- Concurrent Medications (changes since last visit)
- Adverse Events

8.1.2 Evaluations and procedures at Visit 2 (Week 13 ±2)

- Concurrent Medications (changes since last visit)
- Vital signs
- Urine Pregnancy test
- Adverse Events
- Drug Returned
- Drug Dispensed

8.1.3 Evaluations and procedures at Visit 3 (Week 26 ±2)

This is the end of treatment visit for those subjects from study TEN-01-302

- Concurrent Medications (changes since last visit)
- Vital Signs
- Physical Exam (only TEN-01-302 subjects)
- Serum Chemistry and Hematology (only TEN-01-302 subjects)
- Urine Pregnancy Test
- Urinalysis (only TEN-01-302 subjects)
- ECG (only TEN-01-302 subjects)

- Adverse Events
- Drug Returned
- Drug Dispensed (only TEN-01-301 subjects)

8.1.4 Evaluations and procedures at Visit 4 (Week 39 ±2)

This is the end of treatment visit for those subjects from study TEN-01-301

- Concurrent Medications (changes since last visit)
- Vital Signs
- Physical Exam
- Serum Chemistry and Hematology
- Urine Pregnancy Test
- Urinalysis
- ECG
- Adverse Events
- Drug Returned

8.2. Safety Assessments

8.2.1 Safety Assessments

Safety assessments will be based on adverse events, clinical laboratory tests, vital signs, ECG, and physical examinations.

Incidence of adverse events and clinically significant abnormal laboratory values will be determined at the completion of the study. This study will help characterize the safety and tolerability profile of tenapanor 50 mg BID in IBS-C subjects.

Safety assessments are described below.

8.2.1.1 Adverse events

Monitoring of treatment emergent adverse events will be conducted throughout the study beginning on Day 1. Adverse events, including serious adverse events will be recorded in the eCRFs through the end of the study. All adverse events should be followed by the investigator until they are resolved or are clearly determined to be due to a subject's stable or chronic condition or concurrent illness(es). Definitions, documentation, and reporting of adverse events are described in detail in Section 9.

8.2.1.2 Physical examination

A complete physical examination will be conducted during either Visit 3 (TEN-01-302) or Visit 4 (TEN-01-301) (and at any early termination visit).

8.2.1.3 Electrocardiogram

A 12-lead electrocardiogram will be obtained during either Visit 3 (TEN-01-302) or Visit 4 (TEN-01-301) (and at any early termination visit).

8.2.1.4 Vital signs

Vital signs, including heart rate, respiratory rate, sitting systolic and diastolic blood pressure (SSBP, SDBP), temperature, and body weight will be obtained at Visits 2, 3 and 4 (subjects from TEN-01-301 and early terminations only).

8.2.1.5 Clinical laboratory tests

A central laboratory will perform clinical laboratory tests. Blood samples will be drawn from subjects for serum chemistries and hematology at either Visit 3 (TEN-01-302) or Visit 4 (TEN-01-301) (and at any early termination visit). Urine will be taken for urinalysis at either Visit 3 (TEN-01-302) or Visit 4 (TEN-01-301) (and at any early termination visit). A urine pregnancy test will be performed at Visits 2, 3 and 4 (TEN-01-301 only). If the urine pregnancy test is positive, it will be confirmed with a serum pregnancy test. See Appendix A for specific laboratory tests.

Clinical laboratory test values that are considered abnormal will be noted as clinically significant or not clinically significant by the site investigator. Clinical laboratory test values that are out of the normal limits are considered to be abnormal.

Handling and shipment of clinical laboratory samples will be outlined in the Lab Manual.

8.3. Total Blood Volume Required for Study

Table 8-1 Approximate Blood Volume per Subject

Test	Number of Samples	Volume (mL)	Total (mL)
Hematology (blood)	1	3	3
Chemistry (serum)	1	7	7
Total	2	--	10

8.4. Data Quality Assurance

This clinical trial will be monitored according to current Ardelyx Standard Operating Procedures (SOP) or its CRO designee's SOP. Steps to be taken to assure the accuracy and reliability of data include the selection of qualified Investigators and appropriate study sites, review of protocol procedures and the administration of informed consent with the Investigator and associated site personnel prior to study start, and periodic monitoring visits by Ardelyx personnel or its CRO designee. During the trial, the Investigator shall permit Ardelyx or its CRO designee to verify the progress of the trial on site as frequently as necessary. Qualified personnel will review case report form data for accuracy and completeness against source documents during on-site monitoring. Data discrepancies will be resolved with the Investigator or designees, as appropriate. The Investigator shall make the eCRFs and

source documents available, provide missing or corrected data and sign the eCRFs. No personal information will be recorded on the eCRFs in accordance with HIPAA regulations.

An independent Quality Assurance (QA) department, Ardelyx designees and/or regulatory authorities may review this trial. This implies that auditors/inspectors will have the right to inspect the trial center(s) at any time during and/or after completion of the trial and will have access to source documents, including the subject's file. By participating in this trial, Investigators agree to this requirement. Measures will be undertaken to protect subject data handed over by the Investigator to Ardelyx and to inspectors against disclosure to unauthorized third parties and subject confidentiality will be maintained at all times.

9. ADVERSE EVENTS

9.1. Adverse Event

An **adverse event** (AE) is any untoward medical occurrence in a subject administered a pharmaceutical product, whether or not the occurrence has causal relationship with this treatment. An adverse event can therefore be any unfavorable and unintended sign (including an abnormal laboratory finding), symptom, or disease temporally associated with the use of an investigational product, whether or not considered related to the investigational product. This includes any newly occurring event or previous condition that has increased in severity or frequency since the administration of the investigational product.

Worsening of IBS symptoms is not considered an adverse event unless the frequency and/or severity of the symptom(s) are outside of what the subject considers normal for their IBS.

9.2. Severity

The term “severe” is used to describe the intensity (severity) of a specific event (as in mild, moderate, or severe myocardial infarction). Even though the event itself may be of relatively minor medical significance (such as a severe headache), this is not the same as “serious,” which is based on subject/event outcome or action criteria as described above and are usually associated with events that pose a threat to a subject’s life or functioning. A severe adverse event is not necessarily serious. For example, persistent nausea of several hours duration may be considered severe nausea but not meet the definition of a SAE. On the other hand, a stroke resulting in only a minor degree of persistent disability may be considered mild, but would be defined as a SAE based on the above noted criteria. Seriousness (not severity) serves as a guide for defining regulatory reporting obligations.

For both serious and non-serious adverse events, the Investigator must determine the severity of the event using the following definitions:

Mild The event does not interfere in a significant manner with the subject’s normal functioning level. It may be an annoyance but does not cause any limitation in usual activity.

Moderate The event produces some impairment of functioning but is not hazardous to health. It is uncomfortable or an embarrassment and may cause some limitation in usual activity.

Severe The event produces significant impairment or incapacitation and is a definite hazard to the subject's health.

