3.7.1 Adverse Events

Adverse events will be coded using the MedDRA adverse event coding system for purposes of summarization. All adverse events reported will be listed in the data listings. Treatment emergent adverse events (TEAEs) will be tabulated for each treatment cohort and overall. A treatment-emergent AE (TEAE) is any AE that starts on or after the first dose of study drug through the final visit (Visit 3 for subjects from TEN-01-302 and Visit 4 for subjects from TEN-01-301), any event that is considered drug related regardless of the start date, or any event which occurs prior to the first dose of study drug and worsens in severity or is

subsequently considered drug-related by the investigator. An AE is considered drug related if it is possibly related or probably related to study drug.

TEAEs will also be tabulated by whether events are considered related to treatment and by severe severity. Serious adverse events (SAEs) and TEAEs resulting in study discontinuation will be tabulated.

Summarization of AEs will include subject incidence of the following:

- All TEAEs
- Drug-related TEAEs
- Severe TEAEs
- Severe and drug-related TEAEs
- SAEs
- Drug-related SAEs
- Death due to AEs
- TEAEs leading to study drug discontinuation
- Drug-related TEAEs leading to study drug discontinuation

An overall summary table will contain the number and percentage of subjects ever having one of the above listed subsets of AEs. All TEAEs will be summarized for each treatment cohort and overall by MedDRA system organ class (SOC), by SOC and preferred term (PT), and by PT with the number and percentage of subjects. If a subject has more than 1 occurrence of the same TEAE, he/she will be counted only once within that preferred term and system organ class in the summary tables. The most severe occurrence of a repeat TEAE, as well as the closest relationship of the TEAE to the study drug will be used for the analyses.

TEAEs related to study drug, severe TEAEs, SAEs, and TEAEs leading to study drug discontinuation will be summarized in the same manner. That is, summaries will be provided for the numbers and percentages of subjects by SOC, SOC and PT, and PT.

All AEs will be included in by-subject listings. Specific by-subject listings of SAEs and TEAEs leading to study drug discontinuation will be provided. The number of days between first dose and when the event occurred will be presented in listings as well (i.e., relative study day), as will duration of the AE.

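### Protocol 9.2 makes a health hazard a condition of the Severe grade, which conflicts with its own headache example and leaves one or two of six impairment-by-hazard combinations without a grade

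*Protocol*

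**What the plan says.** Protocol 9.2 opens with the concept. The word severe "is used to describe the intensity (severity) of a specific event", and the section separates this from seriousness, which depends on outcome or action criteria. Three examples follow:

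- Headache: "Even though the event itself may be of relatively minor medical significance (such as a severe headache"), with the point that this is not the same as serious.
- Nausea: "persistent nausea of several hours duration may be considered severe nausea but not meet the definition of a SAE".
- Stroke: "a stroke resulting in only a minor degree of persistent disability may be considered mild", although it would be an SAE.

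The section then obliges the investigator to grade every adverse event, serious or not, with three definitions:

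- Mild: no significant interference with functioning. "It may be an annoyance but does not cause any limitation in usual activity". Hazard is not mentioned.
- Moderate: "The event produces some impairment of functioning but is not hazardous to health".
- Severe: "The event produces significant impairment or incapacitation and is a definite hazard to the" subject's health.

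SAP 3.7 names severity as one basis of the safety assessment. SAP 3.7.1 lists severe TEAEs and "Severe and drug-related TEAEs" among its incidence summaries, breaks severe TEAEs down by system organ class and preferred term, and counts the worst grade of a repeated event. The SAP does not restate the grade definitions and has no rule for an event that fits none of them.

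**The concern.** The explanatory text describes one axis, intensity. The definitions use two, functional impairment and hazard to health, and join them so that Severe needs both. An event of minor medical significance is hard to describe as a definite hazard, so text and definition point to different grades for the same headache. Moderate excludes hazardous events, so the three grades also do not cover every event.

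Safety is the only objective, the study is open label with a single treatment, and no testing is planned. The descriptive tables are therefore the result. About 300 subjects at 50 to 60 centers is 300/60 = 5 to 300/50 = 6 per center, so differences between centers in reading the hazard clause would be hard to see in the data. An intense but not dangerous tolerability event, for instance cramping that keeps a subject at home, is the kind that could drop out of the severe rows.

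Severity has a second use. Under SAP 3.7.1 an event that began before the first dose and then worsens in severity becomes treatment-emergent, so the scale also bears on TEAE status.

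**Working it through.** There is no planned figure to reproduce: no sample size, power or event rate bears on this point. The check is to apply the three definitions literally to every combination of the two axes they use.

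Inputs, all from Protocol 9.2:

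- Mild = no limitation of usual activity.
- Moderate = some impairment AND not hazardous.
- Severe = (significant impairment OR incapacitation) AND definite hazard.

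Three impairment levels times two hazard levels gives 3 x 2 = 6 combinations.

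| Impairment | Hazard | Literal grade |
|---|---|---|
| None | No | Mild |
| None | Yes | Mild (hazard is not mentioned) |
| Some | No | Moderate |
| Some | Yes | None: hazard bars Moderate, impairment falls short of Severe |
| Significant | No | Never Severe; none, or Moderate if some includes significant |
| Significant | Yes | Severe |

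Results:

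1. If some excludes significant, 2 of 6 combinations have no grade.
2. If some means at least some, 1 of 6 has no grade.
3. On either reading only 1 of the 2 combinations with significant impairment can be Severe.

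The examples against the table:

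- **Headache.** Minor medical significance places it most naturally in the row for significant impairment without hazard, where Severe is unavailable although the text calls it severe. This is the clearest conflict.
- **Nausea.** The text says only that it may be severe and is not an SAE. It does not say the event is free of hazard, so this is a tension.
- **Stroke.** It may be called mild despite persistent disability, yet Mild allows no limitation of usual activity, and Protocol 9.5 defines disability as substantial disruption of normal life functions. This example also fits its grade badly.

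**The case against.** The strongest reply is that the tables count whatever grade the investigator assigns, and the investigator must assign one. A reader might infer that the severe TEAE tables are wrong, or that events will sit in the data without a grade. The documents support neither. They support a risk of inconsistent grading, and no test or error rate is affected.

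Four further points stand:

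- **Direction.** A reader might infer a net undercount of severe events. A site facing some impairment with a hazard, barred from Moderate, may grade up to Severe. The two gaps can work against each other, so the net effect is not established.
- **Wording.** Severe does not require incapacitation. Significant impairment satisfies that limb.
- **Examples.** It would go too far to say that investigators can never grade the protocol's own examples as severe. A health hazard is not itself an SAE criterion, so an event can be hazardous without being serious.
- **Worsening rule.** It is a route to treatment-emergent status, not to a severe TEAE. A change from mild to moderate qualifies.

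It is also fair that intense events stay visible elsewhere: all AEs are listed, and all TEAEs and those leading to discontinuation of study drug are tabulated. This limits the harm but does not repair the severe rows.

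A last objection is that changing the scale could break comparability with TEN-01-301 and TEN-01-302. Their scales are not in these documents, so this is something to check and not a reason to leave the text as it is.

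**Conclusion.** The concern holds as an internal inconsistency in Protocol 9.2 that the SAP does not repair. Whichever way some impairment is read, a significantly impairing but non-hazardous event cannot be Severe, and an event with some impairment and a hazard has no grade. One or two of the six combinations are ungraded. That range rests on a literal reading and on the three-by-two layout. The combinations are not weighted by frequency, so the count says nothing about the share of AEs affected.

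The supportable consequence is inconsistent grading across sites, and possible under-counting of intense but non-dangerous events in the severe and severe drug-related TEAE tables. The documents give no severity counts, so the size cannot be computed. eCRF guidance that settles the reading may exist, but it is not among the documents. The point deserves correction because these rows are reported results of a study with safety as its sole objective.

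**What to change.** Grade on functional impact alone. In Protocol 9.2, delete the hazard clause from Severe and the no-hazard clause from Moderate, and make clear that Moderate means impairment short of significant. Each of the six combinations then has exactly one grade. A hazardous event without functional limitation, such as a laboratory abnormality without symptoms, would still be Mild. That is intended, because danger is then judged under the SAE criteria in 9.5. Rework the 9.2 examples, the stroke example included, so that they match the definitions, and put the same wording in the eCRF guidance.

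Replacing the conjunction in Severe with an alternative, so that either impairment or hazard suffices, is not an adequate substitute. A hazardous event with no limitation would then meet both Mild and Severe.

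The cost is a short amendment that edits two definitions and the examples, with the written IRB/IEC approval that Protocol 11.5 requires. The severe TEAE count may come out slightly less favourable. Before the change, compare the wording with the TEN-01-301 and TEN-01-302 scales. If any AEs have already been graded, record the date of the change and state in the SAP how grades from before it are handled. No sample size or testing element changes.
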